12.1.2 Descriptive Statistics

Descriptive statistics for continuous variables will include number of participants [n], number and percent of participants with data, mean, standard deviation [SD], median, first and third quartile, minimum and maximum. For categorical variables absolute and relative [%] frequency for categorical data) will be presented.

12.1.3 Handling of Missing Values and of Values outside the Detection Limits

For questionnaire data, total scores and domain or subscale scores may be derived using imputation by averaging across neighboring non-missing variables.

Product use at MT(i) if missing, can be interpolated by averaging across neighboring product use at MT(i-1) and MT(i+1). There will be no imputation for missing CE(i). Only the reported CE(i) will be used in the analysis.

Further details will be provided in the SAP.

12.1.4 Significance Level for Inferential Statistics

No inferential statistics are planned.

12.2 Derived and Computed Variables

12.2.1 Product use

Percent consumption of THS, CC, OTP, e-cig and HnB, respectively, with respect to THSPD, CPD, ePD and OTPD will be calculated at MT_i based on THS Tobacco Sticks, CC, e-cigarettes and OTP reported in Product use questionnaire as:

$$\begin{aligned}\%THS_i &= 100 * \frac{THSPD_i}{THSPD_i + CPD_i + OTPD_i} \\ \%CC_i &= 100 * \frac{CPD_i}{THSPD_i + CPD_i + OTPD_i} \\ \%OTP_i &= 100 * \frac{OTPD_i}{THSPD_i + CPD_i + OTPD_i} \\ \%e-cig_i &= 100 * \frac{ePD_i}{THSPD_i + CPD_i + OTPD_i}\end{aligned}$$

Confidentiality Statement

Data and information contained in this document are considered to constitute trade secrets and confidential commercial information, and the legal protections provided to such trade secrets and confidential information are hereby claimed under the provisions of applicable law. No part of this document may be publicly disclosed without the written consent of Philip Morris Products S.A.

$$\%HnB_i = 100 * \frac{HnBD_i}{THSPD_i + CPD_i + OTPD_i}$$

where CPD_i is the average daily Cigarettes consumption at MT_i , $THSPD_i$ is the average daily THS consumption (Marlboro Heatsticks with iQOS device), $OTPD_i$ is the average daily other tobacco products consumption, $HnBPD_i$ is the average daily HnB products consumption and ePD_i is the average daily e-cigarette products consumption, which is part of the other tobacco products consumption will also be calculated.

Additional percent consumption of tobacco products may be added and will be specified in the SAP.

12.2.2 Definition of Product Use Categories

Product use pattern categories over a period ending at MT_i are defined in Table 4 above.

12.2.3 Sample Size

A total of 4000 participants will be enrolled in the Study. Enrolment will happen in four annual waves.

Assuming an annual drop-out rate of 5% and a maximum of 20% of participants changing from CC smoker or IQOS user to another behavior per year, the person-time pool in each group will be for each annual analysis as described in [Table 16](#):

Table 16 Expected person-time pool for each annual analysis

Wave	Year 1 Report	Year 2 Report	Year 3 Report	Year 4 Report	Year 5 Report
1	375	281	210	157	117
2		375	281	210	157
3			375	281	210
4				375	281
Total (Person-Years)	375	1031	1897	2920	3685

This sample size and the study duration is sufficient for an assumed 1% of participants for a particular period (CB_i ; CB_{i-1}) to estimate this behavior with a precision of less than 1.32% at the first annual analysis and up to less than 0.62% at the final annual analysis.

Confidentiality Statement

Data and information contained in this document are considered to constitute trade secrets and confidential commercial information, and the legal protections provided to such trade secrets and confidential information are hereby claimed under the provisions of applicable law. No part of this document may be publicly disclosed without the written consent of Philip Morris Products S.A.

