1	375	281	210	157	117	1140
2		375	281	210	157	1023
3			375	281	210	866
4				375	281	656
Total (person-years)	375	1031	1897	2920	3685	

This sample size is sufficient to detect for the trajectories analysis, using the assumption of 20% participants switching to another group, an incidence of 1% of participants switching with a precision of less than 1.32% after one year using the first wave at the first analysis and up to 0.62% the final analysis.

Confidentiality Statement

Data and information contained in this document are considered to constitute trade secrets and confidential commercial information, and the legal protections provided to such trade secrets and confidential information are hereby claimed under the provisions of applicable law. No part of this document may be publicly disclosed without the written consent of Philip Morris Products S.A.

TABLE OF CONTENTS

SYNOPSIS.....	33
TABLE OF CONTENTS.....	41
LIST OF IN-TEXT TABLES	42
LIST OF IN-TEXT FIGURES.....	43
LIST OF APPENDICES.....	43
LIST OF ABBREVIATIONS AND DEFINITIONS OF TERMS.....	44
1 ETHICS AND REGULATIONS	49
1.1 Institutional Review Board (IRB) Approval.....	49
1.2 Ethical Conduct of the Study	49
1.3 Participant Information and Consent	50
1.4 Good Epidemiological Practice	50
2 INTRODUCTION	51
2.1 Background	51
2.2 Study Rationale	53
2.3 Anticipated Benefits and Risks.....	53
3 STUDY OBJECTIVES AND ENDPOINTS.....	54
3.1 Main Study Objectives and Endpoints.....	54
4 INVESTIGATIONAL PLAN	57
4.1 Overall Study Design and Plan.....	57
4.2 Rationale for Study Design and Control Group(s)	59
4.3 Appropriateness of Measurements.....	60
4.4 Study Duration	60
4.5 Study Objectives and Endpoints	60
5 STUDY POPULATION	63
5.1 Selection of Study Population.....	63
5.2 Recruitment Strategies and Retention.....	64
5.3 Discontinuation of Participants from the Study.....	64
5.4 Loss to Follow-Up	65
5.5 Violation of Selection Criteria	65
6 RESTRICTIONS AND SUPPORT DURING THE STUDY	66
7 STUDY PROCEDURES	67
7.1 Study Assessments	67
8 SAFETY REPORTING	72

Confidentiality Statement

Data and information contained in this document are considered to constitute trade secrets and confidential commercial information, and the legal protections provided to such trade secrets and confidential information are hereby claimed under the provisions of applicable law. No part of this document may be publicly disclosed without the written consent of Philip Morris Products S.A.

8.1	Definitions.....	72

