4 INVESTIGATIONAL PLAN

4.1 Overall Study Design and Plan

This is a prospective open observational cohort study of Japanese adults, legally authorized to purchase tobacco products in Japan. The Study will describe the patterns of use of tobacco and nicotine containing products and self-reported health outcomes and health related events in CC smokers and IQOS users.

[figure not shown]
Participants will be recruited into the cohort in 4 annual waves of 1000 participants per year (500 IQOS users and 500 CC smokers) until reaching the total study sample size of 4000 participants (2000 per exposure group). The aim of these annual waves is to ensure the recruitment of new IQOS users, as the demographic characteristics of new IQOS users might change over time.

For IQOS users, the date of initiation of IQOS use is the trigger for all study assessments the Study. However the process will be different for CC smokers for whom the questionnaire timing will be based on the date of enrollment. All participants enrolled in the Study will answer the computer assisted self-interviews (CASIs) which will include the following questionnaires: demographic information, core questionnaire (which is a questionnaire including questions about smoking history, detailed product use and intention to stop tobacco and nicotine containing product use), lifestyle assessments, SES, QSU-b, PRI-P, FTND, self-reported health outcomes (symptoms and diagnoses) and health related events (hospitalizations) questionnaire, and cough assessment questionnaire while IQOS users will also be administered the MCEQ and SRCQ. The CASI provider for wave 1 is [REDACTED] and from wave 2 onwards it will be [REDACTED].

Figure 1 Study Design

Confidentiality Statement

Data and information contained in this document are considered to constitute trade secrets and confidential commercial information, and the legal protections provided to such trade secrets and confidential information are hereby claimed under the provisions of applicable law. No part of this document may be publicly disclosed without the written consent of Philip Morris Products S.A.

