4.1.3 Follow-up

During the Main Study the follow-up CASIs will be administered:

Quarterly (every 3 months \pm 4 weeks) for the first 18 months (up to 6 times), at Months 3, 6, 9, 12, 15 and 18,

- Bi annually (every 6 months \pm 4 weeks) for the second 18 months (up to 3 times), at Months 24, 30, and 36,
- Annually (every 12 months \pm 4 weeks), for the last 2 years (up to 2 times), at Months 48, and 60.

The follow-up domain will include the following questionnaires: core follow-up questionnaire, lifestyle assessments, SES, QSU-b, PRI-P, the FTND, self-reported health outcomes (signs, symptoms and diagnoses) and health related events (hospitalizations) questionnaire, cough assessment questionnaire and for IQOS users the MCEQ and the SRCQ as defined in the Schedule of Events.

Participants will complete the follow-up domains online, without the need to attend the Clinical Site or a data collection center.

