5.3 Discontinuation of Participants from the Study

Participants will be informed that they are free to withdraw from the Study at any time. Participants can log into the Study Website at any time to discontinue from the Study. They will be asked to record the reason for discontinuation, although they are not obliged to

Confidentiality Statement

Data and information contained in this document are considered to constitute trade secrets and confidential commercial information, and the legal protections provided to such trade secrets and confidential information are hereby claimed under the provisions of applicable law. No part of this document may be publicly disclosed without the written consent of Philip Morris Products S.A.

disclose it. Data collected for enrolled participants prior to the participant's withdrawal will still be used in the analysis.

Participants may be discontinued from the Study for any of the following reasons:

- Withdrawal of informed consent
- The Sponsor terminates the study. If the Sponsor decides to prematurely terminate the study, the participants and IRB will be promptly informed. Lost to follow-up Participants that discontinue from the study cannot re-enter the study.

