12.4.4 Inferential Analyses

All analyses in this study are descriptive. Therefore, no inferential analysis is planned.

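### Is the stated precision (below 1.32% at the first analysis, below 0.62% at the final one) wrong because it leaves out the plan's own drop-out?

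*Protocol*

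**What the plan says.** Protocol 12.2.3 sets out the loss assumptions first, both as annual rates: "Assuming an annual drop-out rate of 5% and a maximum of 20% of participants changing from CC smoker or IQOS user to another behavior". Table 16 turns these into a person-time pool per group, from 375 person-years at the year 1 report to a cumulative 3685 at year 5. The section then states the precision "for an assumed 1% of participants for a particular period", namely "with a precision of less than 1.32% at the first annual analysis and up to less than 0.62% at the final annual analysis".

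The Synopsis gives the same two figures but words the target differently: "an incidence of 1% of participants switching with a precision of less than 1.32% after one year using the first wave". Protocol 4.1 supplies the wave size: "4 annual waves of 1000 participants per year (500 IQOS users and 500 CC smokers".

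Neither section says whether precision means a half-width, a full width or a distance to one limit. Neither names an interval method, a confidence level or an n. The SAP contains no precision calculation. Its section 10.1.6 makes reported confidence intervals two-sided 95% by default but does not refer to the sample-size statement. In the current protocol text Clopper-Pearson is not mentioned. It survives only in the amendment log, attached to a cardiovascular incidence figure that was deleted.

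Protocol 12.4.4 says "All analyses in this study are descriptive".

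**The concern.** These two percentages are the only quantitative justification of the sample size left in the protocol, so a reader will want to reproduce them. The table beside them does not help, because person-years are not a count of participants observed over one (CBi; CBi-1) interval.

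The figures do come out almost exactly as the distance to the upper 95% limit, with n = 500 in year 1. That is one group's complete first wave. The same section assumes 5% annual drop-out, and applying it would break the year-1 bound. The final figure needs n near 1600, which could be 2000 x 0.80, so the two numbers would also rest on different treatments of loss.

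If this were right, the plan would promise slightly more precision in year 1 than its own assumptions allow. The two descriptions of the 1% (switching after one year, against a particular period) add to the doubt, since follow-up in the early phase is quarterly: "for the first 18 months (up to 6 times), at Months 3, 6, 9, 12, 15 and 18".

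**Working it through.** **Inputs.** p = 1%; drop-out 5% and switching up to 20% a year (Protocol 12.2.3); 500 per group and 1000 in all per wave, 2000 per group and 4000 in all (Protocol 4.1). The 95% level is an assumption borrowed from SAP 10.1.6.

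**Formulas.** With x = 0.01n and z = 1.96:

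- Clopper-Pearson: lower = Beta quantile(0.025; x, n - x + 1), upper = Beta quantile(0.975; x + 1, n - x).
- Wilson: [p + z²/2n ± z·√(p(1-p)/n + z²/4n²)] / (1 + z²/n).
- Wald: p ± z·√(p(1-p)/n).

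**Reproducing the plan's pair.**

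- n = 500: Clopper-Pearson interval 0.325% to 2.318%, upper distance 2.318 - 1 = 1.318%. Wilson upper distance 1.319%.
- n = 1600: interval 0.573% to 1.619%, upper distance 0.619%. Wilson 0.618%.

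Both lie just under the stated bounds. The smallest n with an exact upper distance below 1.32% is 499, so on this measure year 1 tolerates the loss of one participant.

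**Applying drop-out on that measure.**

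- Full year: 500 x 0.95 = 475, interval 0.313% to 2.366%, upper distance 1.366%, or 1.37%. Excess over 1.32%: 0.05 points.
- First quarter only, loss spread evenly (assumption): 500 x 0.95^0.25 = 494, upper distance 1.329%. Excess: 0.01 points.
- Final, one year's loss in each wave: 4 x 475 = 1900, upper distance 0.557%.
- Final, 5% loss for 5, 4, 3 and 2 years: 387 + 407 + 429 + 451 = 1674, upper distance 0.602%.

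The final bound holds either way.

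**Is Table 16 the source?** Year 1 is 500 x 0.75 = 375. The last column adds 117 + 157 + 210 + 281 = 765 to 2920, giving 3685. Used as n, 375 and 3685 give upper distances of 1.613% and 0.377%. The table does not generate the pair.

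**Other 95% readings.**

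| Measure | Year 1 | Final |
|---|---|---|
| Upper distance, Clopper-Pearson | 1.318% (n = 500) | 0.619% (n = 1600) |
| Full width, Wilson | 1.323% (n = 950) | 0.624% (n = 4000) |
| Full width, Wald | 1.319% (n = 875) | 0.617% (n = 4000) |
| Half-width, Clopper-Pearson, no loss in year 1 | 0.996% (n = 500) | 0.523% (n = 1600) |
| Half-width, Clopper-Pearson, after drop-out | 1.026% (n = 475) | 0.477% (n = 1900) or 0.511% (n = 1674) |
| Half-width, Clopper-Pearson, Table 16 pool | 1.177% (n = 375) | 0.336% (n = 3685) |

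The Wilson row uses the whole first wave after drop-out (1000 x 0.95 = 950). It rounds to the stated figures, though it sits slightly above both bounds. The Wald row uses the average of 1000 and 750, which is mean first-year numbers under 25% loss, and meets both bounds. Its n is a construction, as is 1600 in the first row. In the half-width rows both bounds are met with room to spare.

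**The case for a change.** The strongest case for a correction is that the omission is plain on the page and the upper-distance reading is the tidiest. Its n = 500 is exactly one group's first wave, which fits the Synopsis reference to the first wave, and both values fall just inside the stated bounds. Nor can retained data rescue year 1. Protocol 5.3 says data collected before "withdrawal will still be used in the analysis", but a transition needs the later measurement too, and SAP 10.1.4 excludes a participant from any time-point that is missed. Interpolation needs a neighbour on both sides, so it cannot fill in a permanent drop-out. A further point is that the half-width defence depends on pooling. If the final figure meant only the 765 person-years added in the last year, the half-width would be 0.78% and would miss 0.62%.

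The missing definition stands. The claim of an error does not. The upper-distance reading needs an n of 1600 that is printed nowhere, and it has the sponsor ignore all loss in year 1 and then remove only switchers at the end. Mixed conventions of that kind make the reconstruction less certain. For early intervals, retained data keep n near 500, so the year-end value of 1.37% is the least favourable case on that reading. The 765 base is equally unsupported: the totals in Table 16 are cumulative, and that base takes out switchers, who are the events being counted.

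**Conclusion.** No change follows. The plan leaves a term undefined, but no stated figure is shown to be wrong. The drop-out omission can be inferred only by choosing one measure among several that come close. On the common meaning of precision as a half-width, both bounds hold after the plan's drop-out: 1.03% against 1.32% in year 1, and 0.48% to 0.51% against 0.62% at the end.

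On the unfavourable upper-distance reading the year-1 excess is 0.05 percentage points, or 0.01 for a first-quarter interval, and the final bound is still met. These values assume a 95% level, switchers kept in the denominator, and the stated 5% annual loss.

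Nothing turns on a difference of that size. No inferential analysis is planned, and Protocol 12.5 says no decision rests on the annual reports. SAP sections 3 and 8 record that the study was terminated in March 2018 during wave 2 recruitment and that the analysis is restricted to wave 1, so the final precision no longer applies. Intervals in the report will be computed from the participants actually observed. Restated values such as 1.37% would replace an undefined number with one that rests on a measure the plan never chose, and no table, interval or conclusion would differ.

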12.3 Analysis Populations

All participants that enroll in the Study and complete at least one baseline questionnaire (at a minimum the product use questionnaire) as part of the enrollment process will be included and reported as the Study Population.

12.4 Study Analysis

12.4.1 Study Endpoints

See section “Study Objectives and endpoints” for a description of the Study endpoints.

12.4.2 Baseline Comparability

Not applicable.

12.4.3 User Group and Product Use Behavior

See section 12.1.2 “Descriptive Statistics” for a description of the methodology for descriptive statistics in the study.

12.4.3.1 Demographics and Baseline Characteristics

All data will be presented in listings, ordered by baseline usage group and subject, unless otherwise specified. Demographic data include age, sex, occupation, etc.

Descriptive statistics for continuous variables (number of subjects [n], number and percent of subjects with missing data, mean, standard deviation, median, first and third quartiles, minimum and maximum for continuous data, and the n and absolute and relative (%) frequency for categorical data) will be presented by usage group and overall at each time point, where applicable.

12.4.3.2 Product Use Level

To assess objective 1, the following analysis will be conducted.

Summary tables of use of tobacco and nicotine containing products over time for all enrolled participants will be presented by Cohort at baseline, by CB (i) group and overall participants at MT (i) at post baseline, including:

Confidentiality Statement

Data and information contained in this document are considered to constitute trade secrets and confidential commercial information, and the legal protections provided to such trade secrets and confidential information are hereby claimed under the provisions of applicable law. No part of this document may be publicly disclosed without the written consent of Philip Morris Products S.A.

- Mean number of cigarettes smoked (per day) - CPD(i)
- Mean number of THS Tobacco Sticks used (per day)- THSPD(i)
- Mean number of Heat-not-Burn products used (per day)- HnBPD(i)
- Mean number of other cigarettes product used (per day)- OTPD(i)
- Mean number of e-cigarettes used (per day)- ePD(i)
- Percent of THS Tobacco Sticks used (%THS)
- Percent of cigarettes used (%CC)
- Percent of other cigarettes product used (%OTP)
- Percent of e-cigarettes used (%e-cig)
- Percent of Heat-not-Burn products used (%HnB)

The table will be repeated by sex, age group and enrollment wave in the Study. Tables will also be presented by CB.

The following figures will be provided at each measurement time.

- Bar chart of CPD(i), THSPD(i), ePD(i) and OTPD(i) with 95% CI by CB(i-1) and CB(i) group at each measure time MT(i).

Additional statistical analyses will be specified in the SAP.

Corresponding information is provided in participant data listings.

12.4.3.3 Product Use Patterns

The table of current behavior, CB(i), at MT(i) will provide the information of product use patterns.

Summary table of the product use patterns will be evaluated by CE(i) and presented by CB(i) group at MT(i). The product use patterns includes product switching, initiation, re-initiation, quitting attempt, cessation, relapse, consumption changes and product uptake. Additional product transition table will also be provided between CB(i-1) and CB(i). Participants who have tobacco and nicotine product use transitions will be tabulated by previous and current behavior at each study year. The median of time to first product use transitions (behavior switch) will be calculated via Kaplan-Meier estimators and presented by cohort, IB and CB.

The following outputs will be repeated by sex, age group and enrollment:

- Descriptive Statistics of Current Behavior
- Descriptive Statistics of Current Event by Current Behavior
- Descriptive Statistics of Uptake of HnB Products by Current Behavior
- Descriptive Statistics of Transitions Across Behaviors

Additional statistical analyses will be specified in the SAP.

Confidentiality Statement

Data and information contained in this document are considered to constitute trade secrets and confidential commercial information, and the legal protections provided to such trade secrets and confidential information are hereby claimed under the provisions of applicable law. No part of this document may be publicly disclosed without the written consent of Philip Morris Products S.A.

The following figure will also be provided:

- Bar chart of CB(i) group at each measurement time MT(i).

Corresponding information is provided in participant data listings.

12.4.3.4 Quit Attempts

To characterize the quit attempts by cohort at study entry and by CB(i) group at each MT(i) post baseline, the following information will be presented in the:

- Rate and number of self-reported quit attempts
- Characteristics of the quit attempts, including:
 - Length of quit attempt
 - Type of product used to help in quit attempts (if applicable)
 - Reasons for quit attempt
 - Outcome of quit attempt (Success or Restart using tobacco products)

More detail will be given in the Statistical Analysis Plan.

